8.1.3 Instructions for Application

Prior to treatment, the subject's medical history should be obtained, and the subject should be fully apprised of the indications, contraindications, warnings, precautions, treatment responses, adverse reactions, and method of administration.

The subject must be prepared for percutaneous injection using standard methods. The treatment injection site should be prepared with a suitable antiseptic. Apply local or topical anesthesia at the injection site or ice to the area to decrease local swelling/distention or sedation could be used at the discretion of the investigator.

The investigator should locate the initial site for the implant. It is not allowed to inject into scar tissue or into a blood vessel.

ver-correction is not allowed.

It is recommended to mold or massage the injected implant periodically during the injection process to maintain a smooth distribution and integration of the implant.

Following treatment, manual massage of the entire treatment area can be performed by the treating investigator in order to promote even distribution of MRZF111.

The investigator will use the IMD and all investigational materials only within the framework of the clinical investigation and in accordance with this CIP.

8.1.4 Packaging and Labeling

The packaging and labeling will be according to regulatory requirements and specifications in Germany. The labelling that of the outer box is with additional labelling of "Studiennummer: M930521001", and "Medizinproduktenummer: XXXX"(MRZF111 kit number with sequential numbering).

MRZF111 kits will be provided directly to the investigation sites at the beginning of the investigation. Replenishments will be provided during the investigation, if necessary.

8.1.5 Storage of Investigational Medical Device

Storage temperature (a controlled room temperature between 15°C and 32°C) will be controlled once a week and the minimum/maximum temperature will be recorded in a temperature log.

8.1.6 Accountability for Investigational Medical Device

It is the responsibility of the investigator according to German law to ensure that a current record of inventory accountability per site and per investigational subject is maintained. Inventory records must be readily available for inspection by the unblinded investigational monitor and are open to inspection by regulatory authorities at any time. Each shipment of materials for the investigation will contain an MRZF111 kit supply and return form to assist the investigator in maintaining current and accurate inventory records. This form includes the following information: investigation number, dates, quantities, LOT number, expiration date, and the sequential numbering code number assigned to the MRZF111 kit.

Upon receipt of the MRZF111 kits, the investigator according to German law will visually inspect the shipment and verify the number and condition of the IMD. The MRZF111 kit supply and return form will be completed and signed by the investigator or authorized investigation site staff according to local law. The completed form should be sent to the sponsor or the designated warehouse, and the original signed form should be filed with the inventory accountability records.

To ensure proper storage and to verify inventory, a supply inspection will be conducted at regular intervals by the monitor. The results of the inspection will be made available to the authorized individuals (e.g., unblinded monitor, auditor, and regulatory authorities) on request throughout the investigation.

For subject device accountability and treatment compliance, see Section 8.2.5.

8.1.7 Destruction of Investigational Medical Device

Upon the completion or termination of the investigation, all unused MRZF111 kits must be returned to the sponsor or delegated warehouse. The sponsor or warehouse will destroy the MRZF111 kits after completion of the clinical investigation report. Destruction of unused MRZF111 kits at the study site may be possible if written authorization is provided by the sponsor. If destruction at the study site is agreed upon, then a certificate of destruction must be given to the sponsor.

For safety and to prevent cross-contamination, all used disposable needles and cannulas must be discarded in an appropriate sharps or biohazard container. The used IMD has to be destroyed on site too.

8.2 Treatments Administered

MRZF111 will be applied according the administration method described in Section 8.1.3.

8.2.1 Methods of Assigning Subjects to Treatment Groups

The investigation is planned as a multicenter investigation. Subjects will be assigned to treatment groups according to a balanced randomization. Balanced randomization in blocks of appropriate size and blockwise distribution of the IMD to the treatment groups (treatment group A, treatment group B) ensure an approximately equal number of enrolled subjects in every treatment group. The block size will not be disclosed to the evaluators.

The responsible randomization officer will conduct the random allocation of treatments to subjects using a validated computerized randomization program. Subjects will receive the lowest available randomization number, which will be recorded along with the date of randomization in the eCRF.

8.2.3 Selection and Timing of Exposure for Each Subject

8.2.4 Duration of Treatment per Subject

The duration of treatment is approximately 4 months per subject.

8.2.5 Treatment Compliance

At the beginning of the investigation, the site will receive device accountability forms to document how and when MRZF111 is dispensed to subjects or the MRZF111 kit is returned unused to the sponsor or destroyed on site. These forms will be made available to the authorized individuals (e.g., monitor, auditor) and include the following information: investigation number, dates, quantities, and the code number assigned to the MRZF111 kit and investigational subjects.

As the IMD will be injected by the investigator, treatment compliance of the subject is ensured. Dates of treatment need to be documented in the source documentation and the eCRF.

8.2.6 Treatment of Overdose

As treatment with the IMD is performed exclusively in a clinical setting under the supervision of trained medical personnel, the risk of overdose in this investigation is estimated to be low.

However, in the case an overdose occurred (i.e., over-correction), it must be recorded in the source documents and the IMD section of the eCRF and recorded as an AE. Any case of overdose leading to a SAE(s) must be reported to the sponsor in an expedited manner using the appropriate reporting form (see Section 10). Usually, overcorrection is an aesthetic issue and harmless for health. It resolves within six to 12 months without intervention. For the IMD used in this investigation, no antidote has been identified to date, and there is no known established therapy recommended for an overcorrection. The investigator is advised to use best clinical judgment in the unlikely event of an overcorrection with the IMD. Kadouch et al. [Kadouch 2017] recommend treating nodules resulting from overcorrection with massaging, aspiration, intralesional injection with sterile water or corticosteroids.

8.3 Previous and Concomitant Therapies/Procedures

After signature of informed consent and prior to randomization, the subject's medical history should include a detailed list of all medications (including rescue medication) and over-the-counter or prescription, oral or topical, anti-wrinkle or skin enhancer products (e.g., alpha hydroxyl acids, glycolic acids, skin-bleaching agents, retinol, or retinoic acids in the décolleté) the subject was taking for a period of at least 3 months previous to randomization. The record should include the drug name (trade or generic), route of administration (e.g., intravenous, oral), total daily dose/unit (expressed in mg, mL, or International Unit [IU]), indication, the start and stop date (day, month, and year) for each medication, and if the medication is ongoing at the end of the investigation.

Similar information should be collected and assessed for any non-drug therapies that may have an impact on investigational results, e.g., dermal treatments in the décolleté such as toxin treatments, ablative or fractional laser, microdermabrasion, microneedling, chemical peels, non-invasive skin tightening, implantation of non-permanent or permanent dermal fillers, surgical procedures (including implantation of ports, pacemakers or defibrillators and breast augmentation), regardless of time point before randomization.

The medical history including relevant non-drug therapies (as defined in the prior paragraph) have to be documented in the source documentation and the eCRF.

Local anesthetics, sedation or cooling applied prior to or after injection should be documented (please refer to the Section 8.1.3).

The following concomitant medications are forbidden during the investigation:

• During the whole course of the investigation:

• For ten days prior to and three days after treatment (applies to all injection cycles):

The following concomitant non-drug treatments are forbidden during the investigation:

• During the whole course of the investigation:

• For at least 24 hours after treatment (applies to all injection cycles):

• For at least 12 hours after treatment (applies to all injection cycles):

• At the day of a visit before assessments (applies to all visits):

Concomitant medication and concomitant non-drug treatments have to be documented in the source documentation and in the eCRF. This also applies to therapy changes (including changes of regimen) during the investigation.

8.4 Blinding Procedures

8.4.1 Blinding

8.4.2 Planned Unblinding Procedures

This is an open label study with the assessments of the effectiveness of the IMD. There is no planned procedure for unblinding foreseen in this study, and the remain blinded until the end of the study.

8.4.3 Emergency Unblinding

This is an open label study and the treating investigator is unblinded. If a medical emergency occurs and a decision regarding the subject's condition requires knowledge of the number of treatment injection, the treating investigator may disclose to which treatment group the subject belongs.

9 INVESTIGATION ASSESSMENTS AND VISIT SCHEDULE

9.1 Clinical Evaluations

At the beginning of the investigation, the subject's medical history and all relevant current and concomitant medications, therapies and procedures planned during the investigation will be recorded (see Section 8.3) through oral investigation before any IMD injection. A review of this information will allow the investigator to assess whether the subject can be enrolled. Other data will be collected as required, including information obtained from physical examinations, weight, and height. If counseling of subjects is deemed necessary, either prior to enrollment or during the investigation, the following options will be made available: The investigator can refer to other specialists to clarify ambiguous results of the examination during screening period and during the whole course of the investigation.

9.2 Effectiveness Assessments

Any effort should be made that all assessments at the respective investigation site are performed by the same investigator or her/his designated and trained investigation site staff for all subjects enrolled at this site. Who is not delegated otherwise involved in this investigation and who is also not aware of the treatment regimen will perform the MAS endpoint assessments and the investigation. All assessments should be scored in individual subjects by the same rater throughout the investigation. However, if a second rater at the site is qualified, he/she is allowed to perform assessments in absence of the original rater. The name of the treatment in the source data and eCRF.

9.2.3 Biophysical Skin Quality Parameters

9.2.3.1 Cutometer[®] dual MPA 580 – Skin Elasticity

The Cutometer[®] is a standardized device to evaluate elasticity and other biomechanical parameters of the skin. By sucking the skin into the aperture of the probe, the elasticity (capacity of the skin to return in its original position) can be measured by using a non-contact optical measuring system.

The measurement of the Cutometer[®] curve (see Appendix 16.1) and the structure parameters will derive via Cutometer[®] software.

9.2.4 Merz Aesthetics Scales for Décolleté Wrinkles

For the décolleté area in women, two MAS were successfully created and validated for the assessment of the status of wrinkles, which are of importance for aesthetic treatment procedures in this area [Landau 2016]. These two MAS (Décolleté Wrinkles-At Rest, Décolleté Wrinkles-Dynamic)

ill be used in this investigation. Thus, skin wrinkling is evaluated within the décolleté area in both at rest and dynamic positions.

The MAS **Décolleté Wrinkles-At Rest** will be used to assess the severity of wrinkles at rest (see Appendix 16.2).

The MAS **Décolleté Wrinkles-Dynamic** will be used to assess the severity of dynamic wrinkles (see Appendix 16.3).

9.2.5 Treatment Satisfaction Assessments

9.2.5.1 Subject's Treatment Satisfaction Assessment

Subjects will be queried on the level of subject treatment satisfaction (see Appendix 16.4) with the IMD treatment by being asked: "How satisfied or dissatisfied are you with the aesthetic appearance of your décolleté today? Please tick the one option that best fits."

If the subject responds "somewhat dissatisfied", "dissatisfied", or "very dissatisfied", he/she will be asked for additional explanation as to why he/she is not satisfied. Additional explanation, if any, will be kept within the source data and entered at a separate (from the scale) comment field on the eCRF.

9.2.5.2 Investigator's Treatment Satisfaction Assessment

Treating investigators will be queried on his level of treatment satisfaction (see Appendix 16.5) with the IMD treatment in the subject by being asked: "Based on your clinical experience, how satisfied or dissatisfied are you with the current aesthetic appearance of the subject's décolleté? Please tick the one option that best fits."

If the treating investigator responds "somewhat dissatisfied", "dissatisfied", or "very dissatisfied", he/she will be asked for additional explanation as to why he/she is not satisfied. Additional explanation, if any, will be kept within the source data and entered at a separate (from the scale) comment field on the eCRF.

9.2.6 Global Aesthetic Improvement Scales on Décolleté Wrinkles

9.2.6.1 Subject's Global Aesthetic Improvement Scale on Décolleté Wrinkles

The sGAIS-Wrinkles will be used to assess aesthetic improvement in the subjects according to the subjects.

9.2.6.2 Investigator's Global Aesthetic Improvement Scale on Décolleté Wrinkles

The **iGAIS-Wrinkles** will be used to assess aesthetic improvement in the subjects according to the treating investigators

9.2.7 Global Aesthetic Improvement Scales on Décolleté Skin Quality

9.2.7.1 Subject's Global Aesthetic Improvement Scale on Décolleté Skin Quality

The sGAIS-Skin Quality will be used to assess aesthetic appearance of skin quality improvement according to the subjects

9.2.7.2 Investigator's Global Aesthetic Improvement Scale on Décolleté Skin Quality

The **iGAIS-Skin Quality** will be used to assess aesthetic appearance of skin quality improvement in the subjects according to the treating investigators.

9.4 Laboratory Evaluations

A urine pregnancy dip stick test will be performed before each injection visit in women of childbearing potential³. For time points of this assessment please refer to Table 2.

³ Childbearing potential is defined as NOT premenarche, permanently sterilized or postmenopausal (i.e., 12 months with no menses without an alternative medical cause).

9.5 Visit Schedule

The purpose of the baseline visit is to determine subject eligibility for investigation participation. Subjects who are diagnosed with a medical condition during the screening process will be notified and referred for medical care.

Baseline is defined as Day 1/V1 which is the day of enrollment, randomization (preinjection) and first injection of the IMD.

Subjects will be randomized to either treatment group A or treatment group B.

Unscheduled visits may be required in the case of premature discontinuation of investigational treatment and have to be documented in the source data. In this case, a final assessment will be performed. If additional safety follow-up is necessary after this assessment, subjects may be contacted by telephone or assessed on-site, depending on the nature of the follow-up required.

Where a visit to the site is not possible within the allowed time frame due to COVID-19 public health emergency, safety related information (AEs, pregnancy, concomitant medications and concomitant non-drug treatment) should be gathered via telephone

preferably on or around the initially planned date for that visit. Study subjects need to provide prior verbal agreement to this procedure.

CONFIDENTIAL Template: tem-csp-md-v3.0-20181205 File name: M930521001_CIP_4.0_20200610_final

10 SAFETY ASSESSMENTS

10.1 Definition of an Adverse Event (AE)

An AE is any untoward medical occurrence, unintended disease or injury, or untoward clinical signs (including abnormal laboratory findings) in subjects, users or other persons, whether or not related to the IMD.

NOTE 1 This definition includes events related to the investigational medical device or the comparator.

NOTE 2 This definition includes events related to the procedures involved.

NOTE 3 For users or other persons, this definition is restricted to events related to investigational medical devices.

10.1.1 Adverse Event Details

The period of observation for an AE extends from when the informed consent form was signed until the last investigational visit of the subject. Any medical occurrence that happens between the time when the informed consent form is signed and the first treatment with the IMD is an AE and has to be documented in the subject's file and in the eCRF AE report form. Any AE observed will be fully investigated, documented and followed up until the event is either resolved or adequately explained. In cases of surgical or diagnostic procedures, the condition/illness leading to such a procedure is considered as the adverse event rather than the procedure itself. New AEs reported to the investigator during the observational period, after the last treatment with the IMD, must be documented, treated, and followed up like all other AEs.

TEAEs are defined as AEs with onset or worsening at or after the first injection of the IMD.

Pre-existing conditions noted in the medical history and previous to IMD injection should not be reported as an AE, unless the condition worsens, or the disease reoccurs during the reporting period. To determine whether a condition has worsened, it is compared to the condition of the subject at screening.

In case of a positive COVID-19 result, the "COVID-19 infection" has to be documented as an AE in the eCRF. All individual symptoms related to the confirmed COVID-19 infection should be recorded as separate AEs attributable to COVID-19 using the following descriptions e.g. "cough due to confirmed COVID-19 infection".

10.1.2 Adverse Event Handling and Reporting

Data pertaining to AEs will be collected during the telephone contact 24 or at latest 48 hours after each IMD treatment and during each clinical investigation visit based on the subject's spontaneous description, through investigator inquiry, or discovered in the course of examinations done during the visit.

At each clinical investigation visit, the investigator will assess and record any AE in detail in the source data and on the eCRF AE report form. The following information must be recorded:

- AE diagnosis or main symptom;
- Location of AE: outside of injection area, (e.g. systemic) or restricted to injection area. In case of local reaction, the corresponding area should be reported;
- Date of onset;
- Date of worsening;
- Severity (maximum observed; see Section 10.1.3);
- Causal relationship (not related, related);
- Serious (yes or no), date serious since and reason for seriousness;
- Outcome (see Section 10.1.5);
- AE leading to discontinuation of the clinical investigation (yes or no);
- Stop date.

If on-site visits are not possible due to COVID-19 pandemic and the subject provides his/her consent to safety assessments on the phone, safety assessments (AEs, change in medication and non-drug treatment, and occurrence of pregnancy) will be performed via phone calls and the results documented in the source data first and in the eCRF subsequently. For documentation requirements, please refer to section 11.2.

For all adverse events that are collected during telephone visits, it is up to the medical judgement of the investigator to refer a subject to a specialist if deemed necessary, thus ensuring the safety of the subject and the accuracy of the data.

For documentation of a COVID-19 positive test result see Section 10.1.1.

After completion of all scheduled visit assessments the investigator must document any AEs arising from these assessments.

In case of an SAE (defined in section 10.2), the investigator must also complete an SAE report form and report it to Merz and the CRO immediately, as described in Section 10.2.2.

10.1.3 Adverse Event Severity Grading Scale

The clinical severity of an AE will be classified as:

- Mild: Signs and symptoms that can be easily tolerated. Symptoms can be ignored and disappear when the subject is distracted.
- Moderate: Signs and symptoms that cause discomfort and interfere with normal functioning but are tolerable. They cannot be ignored and do not disappear when the subject is distracted.
- Severe: Signs and symptoms that affect usual daily activity and incapacitate the subject, thereby interrupting his/her daily activities.

The Investigator is required to grade the severity/intensity of each AE.

10.1.4 Causal Relationship with Investigational Medical Device

An AE is considered to be "related" to IMD or the injection procedure if a causal relationship between the IMD or the injection procedure and an AE is at least reasonably possible (i.e., the relationship cannot be ruled out). In this case the event is considered an ADE (see Section 10.3). If the event is serious it is a "serious ADE" (SADE) (see Section 10.4).

The expression "reasonable causal relationship" is meant to convey that there are facts (evidence) or arguments to suggest a causal relationship. Otherwise, the relationship should be considered as "not related."

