In accordance with MPSV §5 paragraph (2), SAEs shall be reported to the BfArM immediately using the SAE reporting form for Germany if a causal relationship to the IMD cannot be ruled out. All other SAEs shall be documented completely and reported quarterly or upon request by the BfArM as summary using the MEDDEV 2.7/3 SAE report table. Furthermore, the SAE assessment form provided by the BfArM shall be used. Should no SAEs occur within a defined reporting period, a report shall nonetheless be submitted.

The address for SAE reporting to BfArM is [contact].

In order to ensure reporting of SAEs immediately to the BfArM, the Medical Devices Safety Officer at Merz provides 24 hours availability.

A copy of submitted reports will be provided to the CRO for submission to EC and dissemination to all investigators.

In accordance with MPSV 14 paragraph (1,2), the sponsor and the investigator will take immediately all necessary safety measures to protect immediate or indirect danger in case that circumstances can affect the safety of the subjects, users or third parties. The Medical Devices Safety Officer at Merz will immediately inform the BfArM about these new circumstances and submit the information in addition to the responsible ethics committee.

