12.3.2 Safety Endpoints

12.3.2.1 Secondary Safety Endpoints

• Incidence of TEAEs related to the treatment with the IMD.

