7.2 Safety Endpoints

All safety analyses will be performed on the SES.

AEs will be coded according to the Medical Dictionary for Regulatory Activities (MedDRA) version in effect at the time the database is closed. Only TEAEs will be analyzed, which are defined as AEs with onset or worsening at or after date of first injection of the IMD. Incidences will be calculated for TEAEs on the system organ class (SOC) level and on the preferred term (PT) level (i.e., total and percentage, by intensity, and by relationship). Listings and (as

applicable) tables displaying incidences for TEAEs leading to discontinuation, serious TEAEs, and deaths will also be provided.

Each documented worsening of an AE will be aggregated with the previous corresponding AE record. The start date of the AE will be the date of the record reporting the onset of the AE with the first reported intensity and the stop date will be the last stop date of all aggregated worsening records or considered ongoing, if not yet resolved. For intensity, the worst attribute will be chosen.

CAVE: there is one exception, where an aggregation of the AE with corresponding worsening(s) is not allowed: if the AE record started before the first treatment and the worsening record started (worsened) at or after date of first treatment. In that case, only the AE record(s) starting at or after treatment will be aggregated and regarded as TEAE (see also below).

[figure not shown]
In case of missing intensity or missing causal relationship of an AE the worst case principle will be applied, i.e. a missing intensity will be set to “severe” and a missing causal relationship will be set to “related”. Missing data of the worst outcome will be imputed by “unknown”.

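### Protocol 10.1.4 gives two tests for a related adverse event that conflict when nothing points either way, so the related-TEAE endpoint lacks a single classification rule

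*Protocol*

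**What the plan says.** Protocol 10.1.4 has two paragraphs. Under the first, an AE is related to the device or the injection procedure if causality "is at least reasonably possible (i.e., the relationship cannot be ruled out". A related event is then an ADE, or a SADE if it is serious. The second paragraph explains a reasonable causal relationship as meaning that "there are facts (evidence) or arguments to suggest a causal relationship". It continues "Otherwise, the relationship should be considered as" not related.

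The recorded item in Protocol 10.1.2 is "Causal relationship (not related, related", with no intermediate or unassessable level.

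The endpoint in Protocol 12.3.2.1, repeated in SAP 6.2.2, is "Incidence of TEAEs related to the treatment with the IMD". SAP 6.2.1 gives primary safety endpoints as not applicable. The visible SAP text contains no causality definition. SAP 7.2 says only that a missing causality is set to related.

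Protocol 10.2.2 has three reporting rules:
- Sites report every SAE to the sponsor and CRO immediately, with no causality condition.
- The sponsor reports SAEs to the German authority at once "if a causal relationship to the IMD cannot be ruled out. All other SAEs shall be documented completely and reported quarterly" or on request.
- An SAE that arises after observation has ended need be reported only if the investigator considers it related.

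**The concern.** The two paragraphs resolve uncertainty in opposite directions. Under the first, an event that cannot be excluded as device-caused is related. Under the second, an event with nothing to support causality is not related. Two sites can each follow 10.1.4 and code the same event differently, and the pooled rate then mixes two definitions.

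Little in the design would expose this. There is no control group (Protocol 6.2), the treating investigators are unblinded (8.4.3), and up to 10 sites take part. The 52-week duration is justified partly by late-onset reactions, and an investigator is more likely to be unsure of causality for a late event than for an injection-site bruise.

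Three things are at stake: the count in the related-TEAE endpoint, the ADE or SADE label, and whether the sponsor hears of an SAE that arises after the observation period.

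**Working it through.** **Step 1. Compare the two tests.**

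| What is known about the event | 10.1.4, first paragraph | 10.1.4, second paragraph |
|---|---|---|
| Facts or arguments for causality | related | related |
| Causality excluded | not related | not related |
| Neither | related | not related |

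The tests differ only in the last row. With a binary field, that row has to be forced into one of the two answers.

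**Step 2. Trace what the call controls.**
- Related-TEAE endpoint (Protocol 12.3.2.1, SAP 6.2.2): yes.
- ADE and SADE status (Protocol 10.1.4): yes.
- SAE after the observation period (Protocol 10.2.2): yes, expressly.
- SAE during observation, site to sponsor (10.2.2): no, since all are sent.
- SAE, sponsor to authority (10.2.2): not by its text, since the section states its own criterion, that causality is not excluded. A site's *not related* under the second paragraph can still conflict with that criterion for the same event.
- All-TEAE tables (SAP 7.2): no. "Incidences will be calculated for TEAEs on the system organ class (SOC) level and on the preferred term (PT) level", and relationship is one of the breakdowns.

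**Step 3. Reproduce the plan's safety figure.** Protocol 12.1 gives 100 safety subjects, an event probability of 1.6% and a detection probability of 80%.

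P(at least one) = 1 − (1 − 0.016)^100 = 0.8007, so the 80% reproduces. It concerns any adverse event, and the definition of related does not change it.

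**Step 4. Size the effect on the endpoint.** The number of ambiguous events is not given, so the following are assumptions. Take N = 100 and let k subjects have an ambiguous event as their only related TEAE. The incidence then moves by k/100, or 1 percentage point per subject. With Wilson 95% intervals, z = 1.96, and limits [p + z²/2n ± z√(p(1−p)/n + z²/4n²)] / (1 + z²/n):

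| Assumed base | k = 0 | k = 2 | k = 5 | k = 10 |
|---|---|---|---|---|
| 10% | 10% (5.5–17.4) | 12% (7.0–19.8) | 15% (9.3–23.3) | 20% (13.3–28.9) |
| 30% | 30% (21.9–39.6) | 32% (23.7–41.7) | 35% (26.4–44.7) | 40% (30.9–49.8) |
| 50% | 50% (40.4–59.6) | 52% (42.3–61.5) | 55% (45.2–64.4) | 60% (50.2–69.1) |

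**Step 5. Size the effect on seeing a rare event as related.** Suppose an event with probability 1.6% is coded related in a share f of cases (assumed). Then P(at least one coded related) = 1 − (1 − 0.016f)^100:
- f = 1: 80%
- f = 0.9: 77%
- f = 0.75: 70%
- f = 0.5: 55%

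The event still appears in the all-TEAE tables at the 80% figure. Only its appearance as device-related becomes less likely.

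**The case against.** The second paragraph can be read as explaining the word *reasonably* in the first. It also accepts arguments as well as facts, so it does not demand proof. That narrows the conflict but does not remove it. The first paragraph already carries its own gloss, and that gloss and the second paragraph's fallback give different answers for an event with no argument either way.

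The endpoint is secondary and descriptive. No safety test or threshold is visible, and all TEAEs are tabulated. This stands and limits the consequence. Whether it is the only safety endpoint in the full plan cannot be confirmed, because parts of both documents are not shown.

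A reader might infer three stronger points that the documents do not support:
- **That a *not related* call moves an SAE from immediate to quarterly authority reporting, with a delay of up to three months.** All SAEs reach the sponsor immediately and 10.2.2 has its own trigger. Nothing visible makes the site's binary field that trigger.
- **That two recoded subjects (2/112 = 1.8%) exceed the plan's 1.6%.** The 1.6% is a true event probability for any adverse event, tied to at least 100 subjects. It is not a tolerance for the related-TEAE rate. A recoded event also moves the overall incidence only if the subject has no other related TEAE.
- **That conditions listed in Protocol 4.3.2, such as fever or sarcoidosis, show the conflict.** They are listed as possible reactions to the device. That listing is itself an argument for causality, so they are arguably related under both paragraphs.

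Finally, settling on non-exclusion as the test could draw in weakly connected events. That is a real cost. It is contained if the wording *reasonably possible* in the first paragraph is kept.

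**Conclusion.** The inconsistency is real and confined to 10.1.4. For events with no argument either way, the protocol yields both answers. The related-TEAE endpoint, ADE and SADE status, and the reporting of SAEs after the observation period therefore rest on whichever sentence the site follows. Expedited reporting during the investigation has its own rule. It is affected only in that a site's *not related* may contradict it.

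The size cannot be fixed from the documents. With 100 safety subjects it is 1 percentage point per subject whose only related TEAE is ambiguous. Both the number of such subjects and the base rates in the table are assumptions.

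The rest of the plan leans towards the first paragraph. Authority reporting uses the same test, and SAP 7.2 counts missing causality as related. As written, a blank field counts as related, while a doubtful event assessed under the second paragraph does not. This is a contradiction in how an endpoint is defined. It is worth correcting because correction is cheap, but it does not threaten the trial's main conclusion.

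**What to change.** - **Protocol 10.1.4:** state one classification rule, consistent with both the authority-reporting and the late-SAE rules in 10.2.2. The shortest route is to keep the first paragraph and delete the second, or to reword the second so that its fallback no longer contradicts the first.
- **SAP 7.2:** cite that rule as the definition for the related-TEAE endpoint, next to the existing rule for missing causality.
- **Sites:** send a short clarification stating the single rule.
- **Before database lock:** any causality re-check should cover both *related* and *not related* entries. Querying only the *not related* entries could move the rate in one direction only.

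The cost is one paragraph, one SAP sentence and a site letter, plus queries if a re-check is done. The related-TEAE rate may come out slightly less favourable.
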